3.2 Randomisation

The patient number will be an 8 digits code: 3 digits country code (the study is only conducted in the US, US Country Code is 840), 2 digits site number and 3 digits patient number. Each participating investigative study centre will be assigned a 2 digit investigative study centre number (eg, 01, 02, 03, and up) on enrolment.

Each subject will receive a 3 digit Screening number in sequential order at the Screening Visit after the consent form is signed (eg, 001, 002, 003), regardless of the investigative study centre at which the subject is enrolled.

Enrolled subjects who fail Screening or discontinue study participation early, regardless of whether treatment was received or not, will retain their Screening number and a new number will be assigned to the next enrolled subject.

For subjects who remain eligible after the Screening Placebo Run-In period, randomization numbers (which are separate from the screening numbers) will be assigned by the Interactive Response Randomization System, which is integrated into the Electronic Data Capture (EDC) system. Details of assignment of subject numbers will be provided as a separate document.

Subjects will be randomly assigned to receive litoxetine or matched placebo BID in a 2:1 ratio.

4. Analysis Sets

4.1 Study Populations

The study population will consist of subjects with UI. Subjects must be able to provide written consent and meet all the inclusion criteria and none of the exclusion criteria.

A valid efficacy measurement is defined as a valid number of incontinence episodes as recorded in the bladder diary and uploaded in the eCRF at Visit 2 and Visit 6, i.e. either as 0 or greater than 0.

There are 4 analysis populations for this study:

Randomised population:

Defined as all subjects randomised to treatment (Visit 2).

Safety population:

Defined as all subjects who are randomised to treatment (Visit 2), receive study drug, and undergo at least 1 visit.

Intent-to-Treat (ITT) population:

Defined as all subjects who are randomized to treatment (Visit 2), receive at least one dose of study drug and have a valid efficacy measurement at Baseline (Visit 2).

Per Protocol (PP) population:

Defined as those subjects who are randomised, receive at least one dose of study drug, provide a valid efficacy measurement at Baseline (Visit 2) and a valid end of study primary efficacy endpoint (Visit 6), and have completed the study without a major protocol deviation.

The following populations are defined for analysis purposes:

1. Enrolled Population: each subject that signed the Informed Consent form and entered the Screening Period.
2. Completers Population: each subject that completed the trial, per protocol.
3. Full Analysis Set Population: each subject which is in either ITT or PP population.

4.2 Disposition of Subjects

Subjects randomised and who receive study drug will be identified as completing the study or withdrawn from the study.

The participation of an individual subject may be discontinued prematurely for reasons such as:

1. Withdrawal of written informed consent
2. Required treatment with any medication known or suspected to interfere with the study drug
3. Pregnancy
4. Lack of study compliance
5. Treatment unblinding (treatment unblinding for the purpose of expedite reporting of SUSARs will not by default lead to withdrawal of subjects from the study)
6. Any other condition which in the opinion of the Investigator no longer permits safe participation in the study
7. Protocol Deviation
8. AE
9. Other

4.3 Protocol Deviations

In addition to clinical and study conduct protocol deviations which may include deviations to visit procedure, lab testing and patient safety, the following criteria will be considered as protocol deviations:

1. Study drug compliance less than 80% during Treatment Period of the study
2. Not valid efficacy Endpoint value: Number of incontinence episodes not available at Visit 6 (Endpoint).
3. Not valid efficacy Baseline value: Number of incontinence episodes not available at Visit 2 (Baseline).
4. Prohibited medication and medications to be used with caution taken 30 days prior to study entry (Visit 1) onwards. During the Blinded Data Review meeting the Sponsor will evaluate the medications taken from each patient on a case by case basis, determining if major protocol deviations are found, and if so exclude such subject from the ITT or PP population analysis. The adjudication of prohibited and to be used with caution medications will be provided by the Medical monitor. They include:
 - a. Prohibited medications:
 - Nonselective, irreversible monoamine oxidase inhibitors: eg, moclobemide or linezolid
 - CYP1A2 inhibitors like fluvoxamine, ciprofloxacin, or enoxacin since the combination may result in elevated plasma concentrations of litoxetine
 - CYP2D6 inhibitors like bupropion, fluoxetine, metoclopramide, paroxetine or quinidine since the combination may result in elevated plasma concentrations of litoxetine
 - Pimozide and thioridazine since the combination with litoxetine may result in elevated plasma concentration of these compounds
 - Medicinal products containing duloxetine
 - St John's wort or herbal preparations containing St John's wort (*Hypericum perforatum*)
 - Other serotonergic agents: SSRIs, SNRIs, tricyclic antidepressants like clomipramine or amitriptyline, triptans, tramadol, pethidine, and tryptophan
 - Administration of any other medication that would be considered a safety risk for co administration with litoxetine
 - Any pharmacologic agent used to treat symptoms of urinary incontinence
 - b. Medications to be used with caution:
 - Warfarin or digoxin
 - Benzodiazepines, morphinomimetics, antipsychotics, phenobarbital, sedative antihistamines
 - 1c antiarrhythmics (propafenone, flecainide) and metoprolol
 - Herbal preparations (other than St John's wort mentioned above). However, subjects who have been on a stable dose of these preparations prior to entering the study may continue to take these drugs. No new herbal preparations may be introduced or dosage changes initiated while participating in the study.
5. Days outside the protocol timeframe (protocol allowed time window is ± 2 days) at Visit 6 greater or equal to 8 days will be considered a major protocol deviation. If the number of days outside the protocol timeframe is smaller or equal to 7 the deviation is considered minor.

5. Definitions and Data Conventions

This section contains definitions and conventions that will be used for analysis.

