5.6.1 Allowed Medications

Chronic medications, other than those listed as **Prohibited Medications** (Section 5.6.2), are permitted. However, dosages changes in these medications should, if medically appropriate, not occur while the subject is enrolled in the study. If a dosage change in medication is necessary, information pertaining to the change must be documented in the eCRF. Conventional once-daily multivitamins, acetylsalicylic acid (aspirin) and acetaminophen (Tylenol®), or occasional over-the-counter non-steroidal anti-inflammatory drug (NSAID) compounds (ibuprofen) are permitted during the study.

If a subject is receiving anti-hypertensive medication, then their blood pressure must have been stable over the last 4 weeks on the same dose of anti-hypertensives including, but not limited to, angiotensin-converting enzyme (ACE) inhibitors, diuretics, or β-blockers. If a subject does not meet blood pressure eligibility at Screening, but is otherwise eligible to participate in the study, medication may be added or the dose of medication may be modified if medically appropriate, and the subject rescreened 1 month after the dose adjustment. The change in dosage must be documented according to the instructions in the previous paragraph.

While in the study, doses of anti-hypertensives therapy must not be changed. The only exception to this is a change in dosage that occurs between initial Screening and rescreening as discussed above (ie, the subject's dose of medication changed a month before officially entering the study). The subject should be withdrawn if doses of antihypertensive and/or lipid lowering medications are changed during the study.

Women are permitted to take oestrogen if the dose has been stable over the last 3 months. Men are permitted to take hormone adjuvant therapy if the dose has been stable dose over the last 3 months.

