5.6.3 Medications to be Used with Caution

The following medications should be used with caution during the study:

- Warfarin or digoxin
- Benzodiazepines, morphinomimetics, antipsychotics, phenobarbital, sedative antihistamines
- 1c antiarrhythmics (propafenone, flecainide) and metoprolol
- Herbal preparations (other than St John's wort mentioned above). However, subjects who have been on a stable dose of these preparations prior to entering the study may continue to take these drugs. No new herbal preparations may be introduced or dosage changes initiated while participating in the study.

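### SAP 4.3 item 4 lets a major medication deviation remove a subject from ITT, which neither ITT definition provides for, and it counts permitted caution drugs as deviations

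*SAP*

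**What the plan says.** SAP 4.3 introduces its list by stating that "the following criteria will be considered as protocol deviations". Item 4 of that list reads "Prohibited medication and medications to be used with caution taken 30 days prior to study entry (Visit 1) onwards". Sub-list a repeats the protocol's prohibited drugs. Sub-list b repeats its caution drugs, among them warfarin, digoxin, benzodiazepines, metoprolol and herbal preparations. The Medical monitor adjudicates the medications. The sponsor then looks at each patient individually at the blinded data review, "determining if major protocol deviations are found, and if so exclude such subject from the ITT or PP population analysis". Sub-list b carries an allowance for herbal preparations only: "subjects who have been on a stable dose of these preparations prior to entering the study may continue to take these drugs".

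The protocol separates the two groups of drugs:

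- Section 5.6.1, in the sentence that begins "Chronic medications, other than those listed as", permits chronic medication that is not on the prohibited list.
- Section 5.6.2 bars the prohibited drugs during the study and for 30 days before entry.
- Section 5.6.3 opens with "The following medications should be used with caution during the study" and sets no look-back. Its one firm restriction concerns herbal products: "No new herbal preparations may be introduced or dosage changes initiated while participating in the study".

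**The concern.** There are two separate problems in one SAP item.

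The first, and more important, is the route out of ITT. An ITT set is meant to be fixed by facts settled at or near randomisation, so that the comparison between arms keeps the protection of randomisation. A rule that removes subjects for drugs taken later breaks that, because what a subject takes after randomisation may be a consequence of the assigned treatment. This applies to prohibited drugs as much as to caution drugs.

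The second is the reach of the item. A subject who follows the protocol, for example on stable warfarin, is recorded as a deviator and sent to a review that can end in removal from an efficacy set.

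At stake are the ITT and PP efficacy results and the deviation listings.

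**Working it through.** No stated figure is in question, so the check is a comparison of texts.

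**Step 1. Conditions for entering each set**

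| Set | Conditions | Medication or major-deviation condition? |
|---|---|---|
| ITT, protocol 8.2 | randomised | no |
| ITT, SAP 4.1 | randomised, at least one dose, valid Visit 2 count | no |
| PP, SAP 4.1 | randomised, dosed, valid Visit 2 and Visit 6 counts, study completed, no major deviation | yes |

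Removing a subject from PP for a major medication deviation agrees with its definition. Removing one from ITT agrees with neither ITT definition. SAP 1.5 lists four clarifications of the protocol (a to d), and neither this removal nor the caution-drug rule is among them.

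**Step 2. How each document treats the drugs**

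| Use | Protocol | SAP 4.3 item 4 |
|---|---|---|
| Prohibited drug, on study or in the 30 days before entry | barred (5.6.2) | deviation |
| Caution drug, only in the 30 days before entry | no restriction | deviation |
| Caution drug, stable use on study | allowed with caution (5.6.1, 5.6.3) | deviation, with an allowance for herbals only |
| Herbal preparation started or changed on study | barred (5.6.3) | deviation |

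The documents agree on the first and last rows and differ on the middle two. A benzodiazepine stopped three weeks before Visit 1 meets item 4, although no protocol rule on caution drugs has been broken.

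**Step 3. Which analyses are exposed**

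SAP 1.5 drops mITT, and SAP 6.9 runs efficacy on ITT and PP only. The multiple imputation (SAP 6.1) and the analyses without imputation (SAP 6.9.1) also use ITT. The Full Analysis Set in SAP 4.1 is anyone in ITT or PP, so it does not recover a subject removed from both, and SAP 6.9 does not use it. Safety analyses use the Safety population (SAP 6.3) and are not exposed.

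**Step 4. Why blinding does not settle it**

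Insomnia and anxiety are adverse events of special psychiatric interest (protocol 8.7.1), and giving a concomitant medication is a recognised response to an adverse event (protocol 6.1.2.1.5). A benzodiazepine or sedative antihistamine may therefore be started because of a drug effect. The prohibited list also includes treatments for incontinence itself, and a subject may start one because symptoms have not improved. In either case the medication carries information about treatment or response. A reviewer who does not know the arm but removes such subjects still selects on that information. Medication taken only before randomisation does not raise this problem.

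**Step 5. Size**

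The documents do not say how many subjects take these drugs or how many would be removed, so the bias cannot be sized. For precision alone, take an assumed fraction *f* of the planned 78 randomised subjects, removed equally across arms with unchanged variance. Then 78 × (1 − *f*) remain, and the standard error of the treatment contrast is multiplied by 1/√(1 − *f*).

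| Assumed *f* | Remaining | Standard error × |
|---|---|---|
| 5% | 74.1 | 1.026 |
| 10% | 70.2 | 1.054 |
| 20% | 62.4 | 1.118 |
| 30% | 54.6 | 1.195 |

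These fractions are illustrations. Nothing in the documents supports any one of them.

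**The case against.** The strongest defence has five parts.

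- **Removal is not automatic.** It needs adjudication, an individual assessment under the blind and a finding that the deviation is major. This stands, and it keeps the point minor. However, the SAP gives no rule for when a medication deviation is major, although item 5 gives one in days for Visit 6 timing, and it does not say when ITT rather than PP is the set affected.
- **Someone has to screen the caution drugs.** Protocol 5.6.2 ends with open-ended wording that also prohibits any further drug thought unsafe to give with litoxetine, exclusion 26 repeats it, and protocol 4.3 allows withdrawal for medication thought to interfere with study drug. This stands, and the fix keeps that assessment with the Medical monitor. It does not justify calling every caution-drug use a deviation.
- **The protocol's permission has limits.** Section 5.6.1 discourages dose changes in any chronic medication. A caution drug newly started on study rests on 5.6.3 alone. This stands, so the mismatch is clearest for stable use and for the look-back.
- **Protocol 8.4 is not exhaustive.** It adds to other conduct deviations, and 8.1 leaves further detail to the SAP. This stands, so the silence of 8.4 on caution drugs is not relied on here.
- **The consequence is small.** Deviations are only listed (SAP 6.4), and efficacy is exploratory and secondary. This stands. SAP 6.4 would also show ITT counts by arm, so removals would be visible, though not their cause.

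None of this answers the conflict between item 4 and both ITT definitions.

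**Conclusion.** The point holds and is minor. Item 4 opens a route out of ITT that neither ITT definition contains. Where the medication was started after randomisation, using that route can bias the ITT efficacy analysis. The item also labels as deviations some uses that the protocol allows, and extends to caution drugs a look-back that the protocol applies to prohibited drugs only. The primary safety analysis is unaffected.

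Three stronger readings are tempting, and the documents do not support them:

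- A reader might infer that ITT has no deviation-related condition at all. In fact a missing Visit 2 count is itself a listed deviation (SAP 4.3 item 3) and already bars entry to the SAP's ITT set. That fact is settled before the first randomised dose, so it does not raise the same problem.
- A reader might infer that subjects on stable warfarin or metoprolol will be removed. Nothing says such use would be found to be major.
- A reader might infer a known effect on the result. None can be shown, because the number of users and removals is not given.

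The conclusion rests on reading the removal sentence as written, so that ITT exclusion is a real option at the review.

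**What to change.** Edit SAP 4.3 item 4 before the blinded data review:

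1. Delete *ITT or* from the removal sentence, so that a medication deviation can affect PP only.
2. Limit the item to drugs prohibited by protocol 5.6.2, including any use the Medical monitor finds to be a safety risk under its open-ended wording, plus herbal preparations started or changed during the study (5.6.3).
3. State that other caution-drug use is reported as concomitant medication.

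Dose changes in antihypertensive or lipid-lowering drugs need not be added to the item, because protocol 5.6.1 already deals with them: "The subject should be withdrawn if doses of antihypertensive and/or lipid lowering medications are changed during the study".

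The cost is a wording change to one SAP item. No protocol amendment or new data are needed. The CRF already records these medications (SAP 5.1), and SAP 6.8 already presents concomitant medication in tables and listings, so caution-drug use stays visible.

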8.2 Analysis Populations

There are 4 analysis populations for this study:

Safety population:	Defined as all subjects who are randomised, receive study drug, and undergo at least 1 visit
Intent-to-Treat (ITT) population:	Defined as all subjects who are randomized
Modified Intent-to-Treat (mITT) population:	Defined as all subjects who are randomised, receive at least 1 dose of study drug, and provide an end of study primary efficacy endpoint
Per Protocol (PP) population:	Defined as those subjects who meet the ITT criteria and have completed the study without a major protocol deviation

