1.5 Clarifications from Protocol

- a. Efficacy analysis of nocturia events has been added, although not specifically laid out in the protocol, since this data is captured in the bladder diary and nocturia episodes are of relevance for the wellbeing of the patient.
- b. The protocol includes an mITT population, which has been omitted from analyses since it was determined that the ITT and PP population will adequately describe the data.
- c. The methodology described in the protocol for the efficacy analyses is a mixed model with repeated measures (MMRM). In light of the fact that the efficacy measurements were recorded at visit 2 and visit 6 only, there are no repeated measures. Therefore, the MMRM model described in the protocol cannot be applied to these analyses. The efficacy analyses will be conducted as an analysis of covariance (ANCOVA).
- d. The description of the efficacy endpoints in the protocol is clarified to be:
 - a. Percentage change in number of incontinence episodes that a subject had in a week
This analysis is consistent with the analysis conducted for the phase 2 study IXA CSP 001

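### SAP 4.3 item 4 allows subjects to be removed from ITT for a medication deviation, against both ITT definitions, and leaves their outcome in no planned efficacy analysis

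*SAP*

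**What the plan says.** SAP 4.3 item 4 treats as a protocol deviation "Prohibited medication and medications to be used with caution taken 30 days prior to study entry (Visit 1) onwards". The prohibited list in item 4a includes "Any pharmacologic agent used to treat symptoms of urinary incontinence". At the blinded data review the Sponsor considers each subject's medications, with adjudication by the Medical monitor, "determining if major protocol deviations are found, and if so exclude such subject from the ITT or PP population analysis".

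The analysis sets are defined elsewhere without reference to this rule:

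- Protocol 8.2, ITT: "Defined as all subjects who are randomized".
- SAP 4.1, ITT: "Defined as all subjects who are randomized to treatment (Visit 2), receive at least one dose of study drug", with a valid Visit 2 efficacy value.
- SAP 4.1, PP: among other conditions, subjects must "have completed the study without a major protocol deviation".
- SAP 4.1: "Full Analysis Set Population: each subject which is in either ITT or PP population".

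SAP 1.5 lists the changes from the protocol. Item b drops the protocol's mITT set on the ground that "it was determined that the ITT and PP population will adequately describe the data". It does not mention that ITT may be reduced for medication use.

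**The concern.** ITT is the efficacy set meant to keep the randomised comparison intact, and the protocol synopsis assigns it the primary efficacy analysis. Item 4 adds an exclusion that neither definition contains, so two analysts following SAP 4.1 and SAP 4.3 could build different ITT sets.

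The exclusion can also depend on events after randomisation. A subject who responds poorly may start an incontinence drug, and how often that happens may differ between arms. Removing such subjects selects on something treatment can influence, and the litoxetine/placebo comparison can be biased in either direction.

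The discretion is loosely bounded. SAP 4.3 item 5 gives a numeric boundary between major and minor visit-window deviations, whereas item 4 gives none for medications. Item 4 also covers the caution medications, which protocol 5.6.3 permits.

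**Working it through.** **1. What naming ITT in item 4 does.** A subject judged to have a major medication deviation fails PP under SAP 4.1 whatever item 4 says. Removal from PP therefore adds nothing, and the only new consequence of item 4 is removal from ITT. The wording permits this rather than requires it, and no rule says when it applies.

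**2. Where the excluded subject's outcome could still appear.**

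| Planned use | Set named in the SAP | Outcome included? |
|---|---|---|
| Main efficacy analyses (6.9) | ITT and PP | No |
| Continence proportion (6.9 point 3) | None of its own; general 6.9 rule applies | No, on that reading |
| Sensitivity analyses (6.9.1) | ITT only | No |
| Severity subgroups (6.9.2) | PP only | No |
| Imputation (6.1) | ITT | No |
| Full Analysis Set (4.1) | Union of ITT and PP | No |
| Baseline median for the severity split (6.9.2) | Randomised | Baseline value only |

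No efficacy analysis is assigned to the Completers or Randomised set, and mITT has been dropped. Without item 4, SAP 6.3 would use the subject's recorded or imputed Visit 6 episode count in the ITT analysis.

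**3. Possible size.** The documents give no exclusion rate, outcome level or SD, so this is an illustration.

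- From the SAP: 78 randomised at 2:1, so 78 × 2/3 = 52 litoxetine and 78 × 1/3 = 26 placebo. The endpoint is the log of the Week 8/baseline ratio (6.9 point 1).
- Assumed: retained subjects have a geometric mean ratio of 0.60; k = 1 to 3 excluded subjects, all in one arm, have ratio r between 0.30 and 1.2; SD of the log ratio is 0.6 to 1.0. The site and baseline terms of the ANCOVA are ignored.

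With all n subjects of the affected arm included, its geometric mean is 0.60 × (r/0.60)^(k/n). After exclusion it is 0.60. For placebo exclusions the litoxetine/placebo ratio is multiplied by before/after; for litoxetine exclusions, by after/before.

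| Arm losing subjects | r | k | Mean before | Multiplier |
|---|---|---|---|---|
| Placebo (n = 26) | 1.2 | 1 | 0.616 | 1.027 |
| Placebo | 1.2 | 3 | 0.650 | 1.083 |
| Placebo | 0.30 | 1 | 0.584 | 0.974 |
| Placebo | 0.30 | 3 | 0.554 | 0.923 |
| Litoxetine (n = 52) | 1.2 | 1 | 0.608 | 0.987 |
| Litoxetine | 1.2 | 3 | 0.624 | 0.961 |
| Litoxetine | 0.30 | 1 | 0.592 | 1.013 |
| Litoxetine | 0.30 | 3 | 0.577 | 1.041 |

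If r = 0.60, the multiplier is 1.000 for any k.

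**4. Against sampling error.** SE = SD × √(1/26 + 1/52), which is 0.144 at SD 0.6 and 0.240 at SD 1.0.

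- Placebo, k = 3: shift (3/26) × ln 2 = 0.080 on the log scale, or 0.55 SE (SD 0.6) to 0.33 SE (SD 1.0).
- Placebo, k = 1: shift 0.0267, or 0.18 to 0.11 SE.
- Litoxetine, k = 3: shift 0.040, or 0.28 to 0.17 SE.

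**5. A second set of assumptions.** Suppose 5% to 15% of the litoxetine arm is excluded and their mean log ratio is 0.3 to 0.5 higher (worse) than that of retained subjects. The shift is −(share × difference), from −0.05 × 0.3 = −0.015 to −0.15 × 0.5 = −0.075. The multiplier runs from 0.985 to 0.928, in favour of litoxetine.

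**The case against.** The strongest reply is that little is at stake. Efficacy is secondary and exploratory, and the primary safety analysis uses the Safety population, which item 4 does not touch. Recent use of incontinence drugs is an exclusion criterion (protocol 4.2) and use on study is prohibited (5.6.2), so cases may be few. Part of the item 4 window precedes randomisation, and use in that part cannot depend on arm. Most of the listed drugs are there for reasons other than treating incontinence. Even the most unfavourable illustration stays below one standard error. All of this stands, and it limits the point to one that should be fixed rather than a threat to the trial.

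The decision is also blinded, with medical adjudication, and SAP 6.4 reports ITT counts by arm and lists violations. Blinding prevents choosing by known arm. It does not stop the recorded event from being related to arm. Reporting makes exclusions visible but does not return the outcomes to an analysis.

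Need for an interfering medication is a listed reason for discontinuation (protocol 4.3, SAP 4.2). Some affected subjects may therefore have only an early-termination diary or an imputed value, and item 4 would then discard less Week 8 information than the illustration implies. The contradiction remains.

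The continence denominator in SAP 6.9 point 3 refers to each arm's total at baseline and could be read as all subjects present then. The general 6.9 rule makes ITT and PP the more natural reading, but for that one endpoint the conclusion is an inference.

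**Conclusion.** The concern holds. SAP 4.3 item 4 conflicts with the ITT definition in both documents, SAP 1.5 does not declare the departure, and on the natural reading of SAP 6.9 to 6.9.2 a subject removed under it contributes an outcome to no planned efficacy analysis. This follows from the text and rests on no assumed number.

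The size and direction of any bias cannot be derived from the documents. With one to three exclusions in one arm, the assumed inputs give a multiplier of 0.92 to 1.08 on the litoxetine/placebo ratio (0.97 to 1.03 for a single placebo subject), and none if the excluded subjects resemble those retained. The case for correction is therefore the contradiction and the very small cost of removing it, not a large expected bias. It should be fixed.

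**What to change.** Before unblinding:

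1. Delete the words *ITT or* from SAP 4.3 item 4, so that medication deviations affect PP only.
2. Add one sentence to SAP 4.1: every subject meeting the SAP ITT definition stays in ITT regardless of protocol deviations or concomitant medication, and recorded Visit 6 diary data are used as SAP 6.3 already provides.

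Optionally, add a sensitivity analysis that sets Visit 6 data recorded after a prohibited incontinence drug to missing and imputes them as in SAP 6.1. The covariates of that imputation model would first have to be named, since SAP 6.1 does not list them.

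The cost is two words deleted and one sentence added, with no new data and no required new table. PP still shows the results without subjects who deviated. The edit does not settle a separate difference: the SAP ITT (dosed, valid baseline) is narrower than the protocol's all-randomised ITT, and SAP 1.5 does not declare that either. The same revision could reconcile the two.
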